Overall Study Design: We will partner with community organizations to administer SARS-CoV-2 tests at organized, planned testing events located in communities across Oregon. Sample collection will occur in counties across Oregon and we will collaborate with county public health agencies to determine sites. Samples will be collected using services as usual using a standardized intake form and standardized, EUA authorized sample collection approaches. Data used to evaluate the efficacy of interventions will involve de-identified participant data at the level of the testing site. This study is a randomized clinical trial to test whether ‘Promotores,’ community health workers who deliver culturally-informed set of outreach, education, and engagement interventions, will result in an increase in testing utilization and health behaviors in Latinx communities.

Randomization will occur at the site level such that 18 sites will be randomized to receive the Promotores intervention and 18 will be randomized to receive services as usual. Services as usual include outreach by county public health and community-based organizations (fliers, radio ads, social media, etc.). The promotores intervention includes targeted outreach to Latinx community members and educational direct interactions with participants and distribution of a pamphlet, with the goal of increasing health behaviors and encouraging additional/future testing. The UO will provide support to community-based organizations to employ and train these promotores to assist with recruitment. The promotores will include Spanish speakers, across cultural contexts, living and working in, and intricately connected to, the target community.

- **Outreach as usual description**
 - Basic outreach materials document (flyers, social media posts, radio announcements, etc.)
 - Flyer to promote health behaviors
 - These documents may be modified or not used at all by community stakeholders as they may have other documents they are already using for outreach and health education—these materials are intended to be used for counties who do not have existing or preferred materials
 - See 04c.Services as Usual Materials
- **Promotores intervention description**
 - Basic outreach and flyer to promote health behaviors plus the outlined outreach and health behaviors promotores approaches
 - Promotores training will be provided by the study team
 - See 4d. Promotores Training Outline

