Data points to assess testing site utilization and the health behaviors will include the following:

1. **De-identified protected health information** (from intake forms) from those who engaged in testing (age 3 and older)
 - a. After testing occurs, researchers will have access to de-identified data prepared by the UO’s CLIA laboratory. The data will include four protected health identifiers, site zip code, participant zip code, testing date, and SARS-CoV-2 test result. It will also include demographic data this is not protected health information such as CDC age range, race, and ethnicity. These data will be used to assess outreach activities aimed at increasing participation of Latinx community members in SARS-COV-2 testing. Primary outcomes will be site-level testing rates of Latinx individuals.
 - b. In addition, the study team will record and have access to a list of testing site addresses and testing date, that will be merged with the aggregate file provided by the CLIA laboratory.

2. **Individual level survey data**, collected at NIH-funded testing events from a subset of 3,600 adult participants (age 15 and older).
 - a. Surveys will contain information including demographic information, including address, phone number, and email. This is being collected to link the HIPAA data that we are collecting from the UO CLIA laboratory, in addition to allowing researchers to see if individuals are getting tested in close proximity to their residence. Researchers are looking at population density of Latinx individuals in an area compared to the proportion of Latinx people who attend the testing events. Additionally, the survey will include information about health behaviors to prevent the spread of COVID-19. These data will be collected using an electronic survey that participants can complete on their smartphone, or using an iPad provided on site. If preferred by the participant, the survey may be completed on paper. If the participant prefers or as is needed, the survey items will be read by a field team member, who is bicultural and bilingual. Surveys will be available in Spanish and in English.

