5. **Community Based Organization general outreach activities.** The executive director of each CBO that receives promotores funding will provide a monthly report on the general outreach strategies conducted by the organization. This is a condition of receiving funding, but reports will be included in research reports such as peer reviewed journal articles.

D. Research Population & Recruitment Methods

We anticipate the sample to be comparable with community demographics in each of the testing regions within the counties participating in this study. As we are specifically conducting outreach to encourage Latinx individuals to attend testing events, we expect the overall study population to be 85% Hispanic and 15% non-Hispanic, with 84% of individuals identifying as Caucasian in both ethnic groups and the remaining 16% identifying as African American, Asian, Pacific Islander,

American Indian/Alaska Native, or more than one race. We expect a slight excess of female participants, based on the demographics in the standing population.

- 1. De-identified protected health information participants** will include data from all testing sites participants which will include individuals age 3 and older. We expect approximately 900 people per week will attend a testing event and we will assess outcomes over 40 weeks, thus we expect between 32,000- 36,000 individuals will be included in the testing. Individuals will not be directly recruited to provide these data.

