- 2. Individual level survey data** will include participants who are (a) age 15 years and older; (b) attending an NIH-funded testing event. Exclusion criteria include: (a) individual is unable to understand Spanish or English or another language translated by a qualified translator at a 5th grade level (participants who cannot read will have the consent or assent form read to them); (b) individual discloses that they previously enrolled in the research project. We anticipate up to 3,600 adult individuals will provide survey data. Up to 1,800 individuals will be individuals who had received the promotores intervention and up to 1,800 will have received services as usual. Recruitment will occur at the testing site, by a study research assistant. A standardized recruitment script (see recruitment information document) will be used and will include eligibility questions. Participants will be compensated with a \$30 gift card for each survey they complete (one at baseline, one at one month follow-up for a total of \$60 in gift card renumeration available). To recruit participants, we will also add the following text to testing event flyers circulated by our community partners '\$30 gift cards available for those eligible to participate in a research survey.'
- 3. Anonymous participant interview** will be collected from a sub-set of randomly selected individuals at NIH-funded testing events who are age 18 years or older. We will invite approximately 15 individuals to participate in a brief anonymous interview (5-8 open-ended questions) with a study staff member at our testing events. Anonymous interview data will assist with informing the study about individual behaviors related to attending testing events. We will audio record these interviews for transcription. All audio recordings will be destroyed after transcription activities are complete. A standardized recruitment script will be used, which will provide information about the purpose of the interview and permission for audio recording. Individuals will be compensated with a \$15 gift card for completion of this interview. These anonymous interviews will not be used as research data, and are only to provide feedback on the testing events. This aspect of the study has now been completed.

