#### 4.3.b Embedded AIS Research Questions and Aims

The specific research questions and aims are the following. Question 1a: Is Basic Outreach plus Promotoras Comunitarias more effective for maximizing testing capacity than Basic Outreach? Question 1b: For individuals tested, is Pamphlet plus Promotoras de Salud more effective than Pamphlet only in supporting positive health behaviors for individuals tested? [(A+B+C+D) vs (E+F+G+H)]. Research Aim Question 2: Among slow responding sites, does the mobilization intervention yield an increase in individual positive health behaviors and in site testing capacity? [(D+H) vs (C+G)].

Each of these AIS research questions is depicted in Figures 4.3.2 through 4.3.3:

**Question 1a:** Is Basic Outreach plus Promotoras Comunitarias more effective for testing capacity than Basic Outreach alone, for Latinx communities?

**Question 1b:** For individuals tested, is Pamphlet plus Promotoras de Salud more effective than Pamphlet only in supporting positive health behaviors for individuals tested, and increasing site testing rates?

**Aim 1a:** Is Basic Outreach plus Promotoras Comunitarias more effective for testing capacity than Basic Outreach alone?

**Aim 1b:** For individuals tested, is Pamphlet plus Promotoras de Salud more effective than Pamphlet only in supporting positive health behaviors for individuals tested, and increasing testing rates?

[figure not shown]

Figure 4.3.2

**Research Aim Question 2:** Among slow responding sites, does the mobilization intervention yield an increase in site testing capacity?

**Aim 2:** Among slow responding sites, does the mobilization intervention yield increase in site testing capacity?

[figure not shown]

Figure 4.3.3

In addition to research questions 1 and 2, the SMART design also allows for an omnibus comparison; after starting with Basic Outreach or Basic Outreach + Promotoras Comunitarias, we can examine which of the embedded adaptive intervention strategies is more effective overall for testing capacity and health behavior maintenance [A vs B vs C vs D vs E vs F vs G vs H]. Although not a specific aim of the proposed study, agencies and stakeholders may be particularly interested in this question and our study design will allow us to test this, focusing on the combined R1 and R2 strategies.

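### Question 1b pools all survey participants and adjusts only for the pre-test score, so a possible arm difference in the ethnic mix of attenders, and a possibly smaller effect in non-Latinx people, are left unhandled

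*Protocol*

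**What the plan says.** - **Who is surveyed.** Protocol section D, item 2 admits people aged 15 or older who are "attending an NIH-funded testing event". The exclusions are language and previous enrolment; ethnicity is not a criterion.
- **Expected mix.** The opening of section D says "we expect the overall study population to be 85% Hispanic and 15% non-Hispanic". This is one figure for the whole study. None is given by arm or for the survey sample.
- **What Question 1b asks.** SAP 4.3.b: "For individuals tested, is Pamphlet plus Promotoras de Salud more effective than Pamphlet only in supporting positive health behaviors for individuals tested". SAP 4.3.a lists individual health behaviours as a primary outcome beside site testing rates.
- **The model.** SAP 4.3.d has A1, A2, their interaction and the pre-test covariate. Ethnicity is not named there. Nor is it among the example moderators in Protocol section B, aim 1b, or SAP 4.3.a.
- **What differs by arm before the survey.** Protocol section C, Overall Study Design: "The promotores intervention includes targeted outreach to Latinx community members". Control sites receive outreach as usual. Survey recruitment takes place at the event (section D, item 2).
- **Target of the trial.** Section C asks whether Promotores "will result in an increase in testing utilization and health behaviors in Latinx communities", and item 1a of the data points says "Primary outcomes will be site-level testing rates of Latinx individuals". SAP 4.3.a describes the sampling frame of sites and individuals as Latinx, which does not agree with the open survey eligibility.

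**The concern.** Randomization is by site, and it balances what exists before outreach begins. The survey sample forms afterwards, from whoever comes to the event. One arm adds outreach aimed at Latinx people, and section D itself links the expected mix to outreach. An arm difference in the Latinx share of survey participants is therefore foreseeable, and stratifying sites by county and rurality (SAP 4.3.c) does not prevent it.

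Two consequences follow if the conditions for them are met. If the mix differs by arm and the ethnic groups differ in one-month behaviour beyond what the pre-test score explains, part of the arm contrast is mix and not intervention effect, in a direction that cannot be known in advance. If the culturally tailored session does less for non-Latinx people, the pooled estimate understates the effect in Latinx people. The plan names no covariate, subset or interaction that would reveal or limit either one.

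**Working it through.** **Inputs from the documents.** 36 sites, 18 per arm (Protocol section C); 2,520 people, so 70 per site, intraclass correlation .05, difference .22 at power .80 (last paragraph of SAP 4.3.f); two-sided alpha .05 (SAP 4.3.f); 85% Latinx (section D, applied here to the survey sample as an assumption). The .22 is read as a standardized difference.

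**The SAP's own figure.** With m people per site and SD 1, SE = sqrt(4 × (.05 + .95/m)/36). At m = 70 this is sqrt(4 × .0636/36) = .0840. The detectable difference is (1.960 + .842) × .0840 = .2355, and power at .22 is .745 by normal approximation. The stated .22 at .80 is not reproduced from the stated inputs. It would be if covariates explained about 13% of variance at both levels (.2196, power .801), which the SAP does not say. That is a separate matter, so power is shown on two bases: the SE implied by the SAP, .22/2.802 = .0785, and the recomputed .0840.

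**Dilution.** Pooled effect = .22 × (p + (1 − p) × k), where p is the Latinx share (.85) and k is the non-Latinx effect as a fraction of the Latinx effect (assumed).

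| k | Pooled effect | Power, SAP's SE | Power, recomputed SE |
|---|---|---|---|
| 0 | .85 × .22 = .187 | .66 | .605 |
| .5 | .925 × .22 = .2035 | .736 | .678 |
| 1 | .22 | .80 | .745 |

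**Mix bias.** Bias = (gap in Latinx share between arms) × (ethnic difference in outcome, in SD). Both inputs are assumptions, and the figures are before any reduction by the pre-test score. Type I error uses SE .0840.

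| Gap | Ethnic difference | Bias | Share of .22 | Type I error |
|---|---|---|---|---|
| 0, or any | any, or 0 | 0 | 0 | .05 |
| 10 points | .3 SD | .03 | 14% | .065 |
| 20 points | .5 SD | .10 | 45% | .22 |
| 30 points | .5 SD | .15 | 68% | .43 |

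Thirty points (70% against 100%) is the largest gap possible with equal arms averaging 85%. If the pre-test score absorbed half (assumed), the .03 and .10 would become .015 and .05.

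**Cost of a Latinx estimate.** 85% of 2,520 is 2,142 people, or 59.5 per site. SE = sqrt(4 × (.05 + .95/59.5)/36) = .0856, and .0856/.0840 = 1.019. The detectable difference goes from .2355 to .240, and power at .22 from .745 to .729. The loss is small because between-site variance dominates.

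**The case against.** The strongest reply is that neither mechanism is established. The 85/15 figure is overall. Control sites also serve selected Latinx communities, and SAP 4.3.a describes basic outreach as culturally adapted in its first strategy. The Latinx share shifts only if Latinx attendance rises proportionally more than other attendance. All of this stands. A reader might infer that the intervention does change the mix by arm and that the contrast is confounded. The documents support only that it may be.

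A reader might also infer that the two primary questions address different populations. Item 1a of the data points in section C does restrict testing rates to Latinx individuals, but aim 1a in section B and SAP Question 1a count tests and capacity without that limit. The documents are not uniform enough to support the claim.

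Pooling can be defended: aim 1b speaks of reducing transmission at community as well as individual level, and promotores pass on general public-health information, so no effect at all in non-Latinx attenders is the extreme case. This stands against insisting on a Latinx-only main analysis. It does not remove the need to state the population or to deal with mix by arm.

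The pre-test score helps, but only in part. It is collected at the event, after outreach, and removes only the portion of an ethnic difference that it predicts. The moderator lists are open-ended and could take in ethnicity, but an unnamed possibility is not a pre-specified analysis.

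**Conclusion.** The point holds as a gap in the analysis plan. Open survey eligibility is not the fault, since ethnicity is recorded at intake and can be linked. The fault is that Question 1b neither uses ethnicity nor says whose effect it estimates.

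The size rests on assumptions that the documents cannot settle. Mix bias runs from zero to .15 over the range shown, with .03 at a moderate setting, and less to the extent that the pre-test score absorbs it. Dilution at the stated mix removes at most 15% of the effect, if the non-Latinx effect is not negative, and nothing if the effect is equal in both groups. The change is worth making because the bias is foreseeable, the trial's question is about Latinx communities, and the cost is small.

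**What to change.** In SAP 4.3.d:

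1. Add self-identified ethnicity as a covariate in the Question 1b model for all participants.
2. Pre-specify, as a named analysis, the Question 1b estimate in Latinx participants together with the A1-by-ethnicity interaction.
3. Report the Latinx share of survey participants by arm.

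In SAP 4.3.a and 4.3.b, state the target population of Question 1b and reconcile the Latinx sampling frame with the open eligibility in Protocol section D, item 2. Whether the Latinx set replaces the pooled set as the main analysis is the sponsor's choice of estimand. Recruitment can stay as it is.

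Costs: the Latinx estimate has a standard error about 2% larger on 85% of the sample. Ethnicity should come from the survey's demographic items, and the sponsor should confirm that it is asked there. If it came only from intake data, it would be missing for people who refuse linkage, which section E, item 2 allows without exclusion. Neither adjustment nor restriction removes other arm differences in who attends: Latinx people drawn by promotores may differ from those drawn by usual outreach. The report should state that limit.

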Co-investigators and research assistants will perform research activities within the scope of their training.

Training for research assistants who collect data from participants will be provided by the project coordinator. Training will include how to sanitize devices used for data collection, relevant human subjects training, and standardized processes and procedures for data collection.

Promotores will provide services similar to what they would provide as usual for community-based organization. Given they are part of the research study, but will not be responsible for answering questions about the research or collecting informed consent or assent, and given the possible limited understanding of academic processes and procedures, we are proposing an alternative human subjects training plan for these individuals. Specifically, a researcher with human subjects training will provide human subjects training during the promotores training already being conducted by the research team. All promotores will be added to the research plan and will complete Individual Investigator Agreements (IIA)s if they are not affiliated with the UO. Alternative training procedure and training dates will be documented in the research records.

4. Translator

At least two people who are proficient in Spanish will review all written study materials before providing materials to participating county health departments and community-based organizations.

## 4.3 Statistical Design and Power

### 4.3.a Optimization and Adaptive Research Design

The goal of this research approach is to test optimal strategies to increase SARS-CoV-2 testing in Latinx populations. The primary approach will be a sequential multiple armed randomized trial (SMART). The proposed SMART design will evaluate adaptive intervention strategies (AIS) which vary the testing delivery format and sequence of testing strategies tailored to Latinx communities. Our research will identify an optimal AIS at the site and individual level as well as explore downstream site and individual differences moderators for further personalization. Through the identification of an optimal AIS, our research will provide public health officials and health practitioners with data on specifically what is the most effective and efficient sequence and modal delivery of testing for underserved Latinx communities. Adaptive intervention strategies involve decision rules that specify how the type or intensity of a testing approach should change site response rates during the progress of implementation monitoring.

Moreover, our research design is a hybrid investigation combining effectiveness evaluation and implementation research to further understand what elements of implementation lead to sustainability of the optimal testing strategies. Because each AIS is designed to be a deliverable product for implementation, intervention approaches do not separately involve randomization. Rather, in the implementation of a SMART designed to evaluate these AISs, sites follow a two-stage randomization procedure in order to be assigned to each AIS. All sites are initially randomized to one of the two first-stage interventions. Sites are then re-randomized to one of the two second-stage intervention strategies. This randomization procedure allows an evaluation of the relative effectiveness of each overall AIS as well the ability to explore other questions such as which first-stage intervention is the most effective and which second-stage intervention format is the most effective for slow-responding sites. Unique analytic strategies are used to maximize power to address these questions within SMART designs (see Statistical Analysis Plan below).

Within the SMART, a measure of initial response is assessed following implementation of the primary outreach approaches in order to evaluate each site's need for further adaptation. In this way, testing is tailored to meet the needs of communities and their Latinx individuals and families by providing enhanced testing strategies to slow-responding sites. This measure of initial response is referred to as a primary tailoring variable. In the proposed study, the primary tailoring variable is whether a site is operating at a threshold of 80% testing capacity, based on the frequency and per capita testing rates and presumption of 50 tests per testing event. The AIS each represent distinct plans of testing outreach approaches. Within the SMART, it is then possible to evaluate which adaptive sequence is the most effective in impacting Latinx testing rates and secondary outcomes such as health maintenance behaviors.

Specifically, the proposed RADx SMART includes 4 embedded adaptive intervention strategies (AIS). Sites and individuals in the proposed Latinx sampling frame will receive one of two first-stage implementation outreach strategies: Basic Outreach approaches or Basic Outreach plus Promotoras Comunitarias. Primary outcomes will be site level testing rates and individual level COVID-19-related health behaviors. After the initial 4 weeks (2 testing events), sites will be re-randomized in the second-stage randomization to either stay the course stationary events or to a mobilization intervention. Thus, for the primary criterion outcome of testing capacity, the SMART design includes 4 embedded site level adaptive intervention strategies (AIS): (1) starting with culturally adapted Basic Outreach, and staying the course; (2) starting with Basic Outreach followed by mobilization intervention; (3) starting with Basic Outreach plus Promotoras Comunitarias and staying the course; and (4) starting with Basic Outreach plus Promotoras Comunitarias plus mobilization intervention. In addition, as a booster to the Promotoras Comunitarias intervention, for health behavior outcomes, individuals tested at Basic Outreach sites will receive pamphlet health promotion pamphlets, and those tested at Promotoras Comunitarias sites, will receive a health pamphlet plus a Promotoras de Salud intervention.

[figure not shown]

Figure 4.3.1

The use of a primary tailoring variable representing initial response allows the AIS to be responsive to individual Latinx family needs for effective testing. Secondary tailoring variables represent an additional approach to more deeply personalize AIS. Secondary tailoring variables include site or individual characteristics (i.e., moderators) and are used to examine the overall adaptive intervention strategies most likely to be effective from individual differences perspectives. Potential secondary tailoring variables are measured at baseline and evaluated following completion of the study for their ability to predict differential response to each AIS. For example, the SMART could reveal that sites in more socially disadvantaged communities or individuals with greater perceived stigma may benefit most from AIS 4 involving two Promotoras interventions allowing for maximum engagement outreach. Secondary tailoring variables, or identified moderators can be utilized for further adaptation in future implementation roll out. The study design is depicted in Figure 4.3.1 above.

